### **14.3.1 Sample Size and Statistical Power**

The historic control used for comparison is based on data published by Judson et al. Patients with advanced or metastatic soft tissue sarcoma treated with single agent doxorubicin had a median PFS of 4.6 months. We consider a median PFS of 3.7 months (safety margin of 20%) to be non-inferior to the PFS seen in patients treated with doxorubicin alone. We will be using a one-sided log-rank test at an alpha level of 0.05 with a power of 0.80 to determine if treatment of doxorubicin with upfront dextrazoxane is non-inferior to doxorubicin alone.

[figure not shown]
A maximum of 65 patients may be enrolled to allow for a 10% dropout rate, resulting in at least 57 patients for testing of the primary endpoint. Using 57 patients, we have 0.80 power at a 1-sided significance level of 0.05 to detect a median PFS 3.7 months compared to this historic control's PFS of 4.6 months.

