## **3.0 PATIENT SELECTION**

At least 57 but up to 65 patients will be enrolled in this study to receive dextrazoxane concurrently with standard of care doxorubicin. At the completion of accrual, an additional 10 patients meeting the eligibility criteria below will be enrolled as a control group for the correlative studies as there is no baseline data for these tests; these patients will receive institutional standard of care therapy.

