### **14.2 Primary Endpoint**

We are comparing the progression-free survival (PFS) rate of patients being treated with doxorubicin in combination with dextrazoxane to a historic control established by Judson et al in 2014. PFS is defined as the time from randomization to the first occurrence of progression or death due to any cause. If no event exists, the PFS will be censored at the last scheduled disease assessment on study. Patients who have reached their maximum follow-up and have remained progression-free will be censored for progression at the date of their last disease assessment. Intention to treat principles will be used for analyzing the primary endpoint. The primary endpoint will be tested using estimates of median PFS and 95% confidence intervals derived from Kaplan-Meier models.

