### **14.3.2 Continuous Monitoring Rule to Evaluate for Early Progression**

The expected rate is 50%, maximum allowable rate is 70%. Total number of patients is 63, including 10% for withdrawal or loss to follow up. The desired probability of stopping at a rate of 50% (incorrect early stopping) is  $\leq 0.05$ . The desired probability of stopping at a rate of 70% (correct early stopping) is 0.80.

If the true rate is 50%, then the calculated probability of incorrect early stopping is 0.05. If the true rate is as high as 70%, the calculated probability of correct early stopping is 0.88.

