### **14.3.3 Maximum Accrual**

Maximum accrual in the treatment group is 63 patients, which includes 10% over the accrual to replace those patients deemed ineligible due to improper histology having been determined on the basis of information available prior to randomization. Accrual to the control group is 10.

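### The stated 0.80 power with 57 patients does not follow from the inputs in 14.3.1: under exponential PFS it is about 0.50 for the log-rank test named there, and lower for the Kaplan-Meier interval named in 14.2

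*Combined protocol and SAP*

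**What the plan says.** Section 14.3.1 gives the design inputs. The historical reference is fixed: "Patients with advanced or metastatic soft tissue sarcoma treated with single agent doxorubicin had a median PFS of 4.6 months". A median of 3.7 months, described as a 20% margin, is the non-inferiority limit. The test is specified as "We will be using a one-sided log-rank test at an alpha level of 0.05 with a power of 0.80". The sample-size statement is "Using 57 patients, we have 0.80 power at a 1-sided significance level of 0.05 to detect a median PFS 3.7 months". Section 14.1 says the primary endpoint is tested only in the dexrazoxane cohort, so this is a one-sample comparison with a fixed historical value.

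Section 14.2 describes the primary analysis differently: "The primary endpoint will be tested using estimates of median PFS and 95% confidence intervals derived from Kaplan-Meier models". It mentions neither a log-rank test nor 3.7 months.

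The size of the treatment group also varies. Section 3.0 has "At least 57 but up to 65 patients will be enrolled in this study" and 14.3.1 has "A maximum of 65 patients may be enrolled to allow for a 10% dropout rate". Section 14.3.2 has "Total number of patients is 63, including 10% for withdrawal or loss to follow up", its monitoring table ends at patient 63, and 14.3.3 has "Maximum accrual in the treatment group is 63 patients".

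**The concern.** Medians of 4.6 and 3.7 months are close: a hazard ratio of about 1.24. A log-rank test draws its information from events, and 57 patients supply at most 57. That is few for a ratio this near 1, so 0.80 power looked too high.

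The two sections also appear to give two decision rules that differ in method and in error rate, since the lower end of a 95% interval is nominally a one-sided 0.025 criterion. The same data could pass one and fail the other.

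The 0.80 figure is the readable justification for the primary sample size. If it is wrong, a failure to show non-inferiority would be likely even if dexrazoxane costs no efficacy, and could be misread as evidence that it does.

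**Working it through.** **Inputs.** From 14.3.1: historical median 4.6 months, limit 3.7 months, one-sided alpha 0.05, log-rank test, 57 patients, stated power 0.80. From 14.1: a single tested cohort. From 5.5: follow-up of up to five years, so at these medians nearly every patient has an event. Assumptions not in the readable text: exponential PFS, and 4.6 months known without error. Counting all 57 patients as events is the most favourable case for 57 patients.

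**Attempt to reproduce 0.80 (null 3.7, truth 4.6).** Effect: ln(4.6/3.7) = 0.2177, a hazard ratio of 1.243.

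- Events needed: (1.645 + 0.842)² / 0.2177² = 130.4. With a margin of exactly 20% (3.68 months) the count is 124.2.
- Power with d events: Φ(√d × 0.2177 − 1.645). For d = 57, √57 × 0.2177 = 1.644, almost exactly the critical value, so power is 0.50.
- d = 63 gives 0.53; d = 65 gives 0.54; d = 51 (about 10% lost) gives 0.46.

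**Checks on the approximation, 57 patients, one-sided 0.05.**

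| Variant | Power |
|---|---|
| Exact exponential test (chi-square, 114 df), null 3.7, truth 4.6 | 0.52 |
| Same test reversed, null 4.6, truth 3.7 | 0.47 |
| Median ratio taken as exactly 0.80 | 0.52 |
| Simulated one-sample log-rank, several variance forms | 0.485 to 0.546 |
| Two-sample log-rank, 57 events in total | 0.21 |
| Two-sample log-rank, 57 events per arm | 0.31 |

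None comes near 0.80. The reversed row is included because the last sentence of 14.3.1 can be read that way.

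**What 57 events would support at 0.80.** Detectable ratio: exp(2.4865/√57) = 1.390. That corresponds to a margin of 4.6/1.390 = 3.31 months, or to the 3.7-month margin if the true median is 3.7 × 1.390 = 5.14 months.

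**Which changed inputs would give 57 and 0.80.** One-sided alpha 0.20 with a ratio of exactly 0.80 needs 56.9 events, but the text says 0.05. A Weibull shape k multiplies the effect by k, so power is Φ(√57 × k × 0.2177 − 1.645): 0.34 at k = 0.75, 0.66 at k = 1.25 and 0.79 at k = 1.5. Reaching 0.80 needs k = 1.51.

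**The 14.2 analysis.** Section 14.2 states no success criterion. The natural one is that the lower 95% limit of the median exceeds 3.7 months.

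- A log-rank test at the matching one-sided 0.025 has power 0.38 with 57 events and needs about 166 events for 0.80.
- For the Kaplan-Meier interval itself, without censoring, S(3.7) = 0.5^(3.7/4.6) = 0.573 when the true median is 4.6. The lower limit clears 3.7 months if at least 36 of 57 patients are event-free then (plain or log interval), or 37 of 57 (log-log). The binomial probabilities are 0.223 and 0.151; simulating the interval gave 0.225 and 0.152.
- At k = 1.5, S(3.7) = 0.607 and the plain-interval power is still only 0.40.

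**Accrual.** Allowing 10% dropout, 63 × 0.9 = 56.7 and 65 × 0.9 = 58.5. Whichever was meant, the sections disagree, and patients 64 and 65 would have no monitoring boundary.

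**The case against.** The strongest objection is that 14.3.1 never says PFS is exponential, and that a figure not reproduced in the text available for review sits between the test specification and the 57-patient sentence. With a Weibull shape of about 1.5 (about 1.42 with 65 events), the log-rank test does reach 0.80. This stands as a limit on the claim: the shortfall is shown under exponential PFS, and the figure may hold another assumption. It cannot raise the number of events above the number of patients, and even at shape 1.5 the Kaplan-Meier criterion stays near 0.40.

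Second, the intention-to-treat set could contain up to 65 patients, so 57 is not a strict ceiling on events for the trial. That is fair, but 65 events give only 0.54.

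Third, the criterion attached to 14.2 is inferred. The exact error rates of the 36-of-57 and 37-of-57 rules at a true median of 3.7 are 0.031 and 0.017, so 0.025 is nominal. Section 14.3.1 does tie the log-rank test to the non-inferiority decision. These points stand, but 14.2 still says the primary endpoint is tested another way, and nothing reconciles the two.

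Fourth, on the reversed reading non-inferiority would be inferred from failing to reject 4.6 months, and a regimen as good as the control would rarely fail. But with power 0.47, a true median of 3.7 months would then go undetected about 53% of the time (1 − 0.47), so 0.80 is wrong there too.

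**Conclusion.** The concern holds. From the readable inputs, with exponential PFS, a fixed 4.6-month reference and one event per patient, the one-sided 0.05 log-rank test with 57 patients has power of about 0.50, not 0.80; about 130 events would be needed. Across the one-sample variants at 57 events the range is 0.47 to 0.55. For the Kaplan-Meier interval of 14.2, read as a lower limit above 3.7 months, power is about 0.22 (plain or log) or 0.15 (log-log). Confidence is high for this conditional statement; an undisclosed non-exponential shape could change the log-rank figure. The mismatch between 14.2 and 14.3.1 does not depend on that assumption. This needs correction because it concerns both the decision rule and the sample-size justification of the primary endpoint. The 63-versus-65 discrepancy is separate and minor.

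**What to change.** 1. Choose one decision rule for the primary endpoint, with 3.7 months as the null value, and state it identically in 14.2 and 14.3.1. If the interval is kept, name its type and the success criterion.

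2. Restate power for that rule with its survival assumption.
   - For the one-sided 0.05 log-rank test: assuming exponential PFS and 57 events, power is about 0.50 against a 3.7-month margin if the true median is 4.6 months; 0.80 power would hold for a margin of about 3.3 months (hazard ratio 1.39), or for the 3.7-month margin if the true median is about 5.1 months.
   - For the Kaplan-Meier 95% interval: assuming exponential PFS, 57 patients and no censoring, the chance that the lower limit exceeds 3.7 months is about 0.22 (0.15 with a log-log interval) if the true median is 4.6 months.
   - If 0.80 rests on another assumption, state it in the text.

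3. Use one maximum accrual for the treatment group in 3.0, 14.3.1, 14.3.2 (including its table) and 14.3.3.

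The cost is protocol wording only, with no added patients, visits or data. The stated power becomes less favourable.

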### **14.3.2 Continuous Monitoring Rule to Evaluate for Early Progression**

The expected rate is 50%, maximum allowable rate is 70%. Total number of patients is 63, including 10% for withdrawal or loss to follow up. The desired probability of stopping at a rate of 50% (incorrect early stopping) is  $\leq 0.05$ . The desired probability of stopping at a rate of 70% (correct early stopping) is 0.80.

If the true rate is 50%, then the calculated probability of incorrect early stopping is 0.05. If the true rate is as high as 70%, the calculated probability of correct early stopping is 0.88.

### Continuous monitoring of early progression and death

A table and reference are on the following page.

Suspend for review if # early progression events or deaths EXCEEDS:	In the first ____ patients:
2	2
3	3
4	4
5	5
6	7
7	8
8	10
9	11
10	13
11	14
12	16
13	17
14	19
15	20
16	22
17	23
18	25
19	27
20	28
21	30
22	32
23	33
24	35
25	37
26	38
27	40
28	42
29	43
30	45
31	47
32	49
33	50
34	52
35	54
36	56
37	57
38	59
39	61
40	63

Reference:

Ivanova A, Qaqish BF and Schell MJ. (2005). Continuous Toxicity Monitoring in Phase II Trials in Oncology. *Biometrics* 61, 540-545.

### **14.3.3 Maximum Accrual**

Maximum accrual in the treatment group is 63 patients, which includes 10% over the accrual to replace those patients deemed ineligible due to improper histology having been determined on the basis of information available prior to randomization. Accrual to the control group is 10.

## APPENDIX A: ECOG Performance Status Scale

Grade	Description
0	Normal activity. Fully active, able to carry on all pre-disease performance without restriction.
1	Symptoms, but ambulatory. Restricted in physically strenuous activity, but ambulatory and able to carry out work of a light or sedentary nature (e.g., light housework, office work).
2	In bed <50% of the time. Ambulatory and capable of all self-care, but unable to carry out any work activities. Up and about more than 50% of waking hours.
3	In bed >50% of the time. Capable of only limited self-care, confined to bed or chair more than 50% of waking hours.
4	100% bedridden. Completely disabled. Cannot carry on any self-care. Totally confined to bed or chair.
5	Dead.
